8.5.1 Determination of drug concentration

Samples for determination of selumetinib and N-desmethyl selumetinib concentration in plasma will be analysed by Covance on behalf of AstraZeneca, using an appropriately validated bioanalytical method. Full details of the analytical method used will be described in a separate Bioanalytical Report.

Incurred sample reproducibility analysis, if any, will be performed alongside the bioanalysis of the test samples. The results from the evaluation will not be reported in the CSR but separately in a Bioanalytical Report. CONFIDENTIAL AND PROPRIETARY 84 of 183 Selectivity (in a patient population) analysis, if any, may be performed alongside the bioanalysis using PK pre-dose samples. The results from the evaluation will not be reported in the CSR, but separately in a Bioanalytical Report.

8.5.2 Storage and destruction of pharmacokinetic samples

Pharmacokinetic samples may be disposed of or destroyed and anonymised by pooling. Additional analyses may be conducted on the anonymised, pooled PK samples to further evaluate and validate the analytical method. Any results from such analyses may be reported separately from the CSR.

Pharmacokinetic samples will be disposed of after finalisation of the Bioanalytical Report.

8.6 Pharmacodynamics

Pharmacodynamic parameters are not evaluated in this study.

8.7 Genetics

Genetic testing is not evaluated in this study.

8.8 Biomarkers

Biomarkers are not evaluated in this study.

8.9 Health economics or medical resource utilisation and health economics

Health economics/medical resource utilisation and health economics parameters are not evaluated in this study.

9. STATISTICAL CONSIDERATIONS

9.1 Statistical hypotheses

No formal statistical hypotheses will be tested.

9.2 Sample size determination

The primary objectives are to evaluate the safety, tolerability and PK of selumetinib. Approximately 16 paediatric and 16 adult subjects with NF1 and inoperable PN will be enrolled in the study to obtain adequate PK and safety data. Per the Chinese Phase 1 PK guideline, at least 8 to 12 subjects per cohort are required. To allow for dropouts and nonevaluable cases, 16 subjects in each cohort will be enrolled. There must be a minimum of 6 subjects each in the 3 to 11 and 12 to 17 year age groups at the time of enrolment.

9.3 **Populations for analyses**

Population	Description
Safety analysis set	The safety analysis set consists of all subjects who receive at least 1 dose of selumetinib.
Pharmacokinetic analysis set	All subjects who receive at least 1 dose of selumetinib and have at least 1 post-dose evaluable concentration-time data point.

For purposes of analysis, the following populations are defined:

9.4 Outcome measures for analyses

9.4.1 Calculation or derivation of pharmacokinetic variables

PK analysis of the plasma concentration data for selumetinib and N-desmethyl selumetinib will be performed by AstraZeneca or a Contract Research Organisation on behalf of AstraZeneca. The actual sampling times will be used in the parameter calculations and PK parameters will be derived using standard noncompartmental methods.

Where possible, the following PK parameters will be determined with plasma concentration data of selumetinib and N-desmethyl selumetinib: AUC, AUC₀₋₁₂, AUC_{0-t}, C_{max} , t_{max} , and $t_{1/2}$ after a single dose, and AUC_{0-12,ss}, $C_{max,ss}$, and Rac (for AUC and C_{max}) after multiple doses.

The C_{max} , $C_{max,ss}$ and t_{max} will be determined by inspection of the concentration-time profiles. The $t_{1/2}$ will be calculated as $ln2/\lambda z$, where λz will be calculated by log-linear regression of the terminal portion of the concentration-time profiles where there are sufficient data. The AUC₀₋₁₂, AUC_{0-12,ss}, and AUC_{0-t} will be calculated using the linear/log trapezoidal rule (i.e. "linear-up-log-down": the linear trapezoidal rule is used any time that the concentration data are increasing, and the logarithmic trapezoidal rule is used any time that the concentration data are decreasing). Where appropriate, the AUC_{0-t} will be extrapolated to infinity using λz to obtain AUC. The Rac (AUC) and Rac (C_{max}) will be calculated as the ratio of the AUC_{0-12,ss} or $C_{max,ss}$ following multiple dosing by the AUC₀₋₁₂ or C_{max} following the first dose, respectively.

9.4.2 Calculation or derivation of safety variables

Safety and tolerability will be assessed in terms of AEs, clinical safety laboratory assessments, physical examination, vital signs, weight/height, ECG, echocardiogram, performance status, and ophthalmologic assessment for both paediatric and adult cohorts. For the paediatric cohort only, bone growth assessments and Tanner stages will also be collected.

9.4.3 Calculation or derivation of efficacy variables

9.4.3.1 Tumour response

9.4.3.1.1 Objective response rate

Objective response rate (ORR) is defined as the proportion of subjects who have a CR or confirmed PR (defined as target PN volume decrease $\geq 20\%$ compared to baseline and confirmed by a consecutive scan within 3 to 6 months after first response), as determined by independent central review and investigator per REiNS criteria.

Best overall response (BOR) is defined as the best response recorded from the start of the treatment until progression or the last evaluable MRI assessment in the absence of progression.

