PNs in NF1 patients are histologically benign Schwann-cell tumours (Wu et al 2005; Rutkowski et al 2000) that, depending on the location and the growth rate, bear all the characteristics typical of cancers. There is a high unmet medical need for patients with NF1 and inoperable PN as there are no approved medical treatments to cure, prevent or reverse the disease. A number of medical treatments have undergone evaluation in early clinical studies for subjects with NF1-related PNs, but these studies have reported only moderate to no clinical activity, and no systemic therapy has been shown to induce consistent and durable tumour shrinkage. Since these relentlessly growing tumours induce co-morbidities that impact children from early childhood through adolescence and their entire lifespan, patients with inoperable and progressive PNs suffer from a significant unmet medical need. There are no epidemiological data to estimate the actual incidence or prevalence of NF1 in China. It is believed that the clinical picture of NF1, including NF1 and inoperable PN, in China is in line with that observed globally. Debulking surgery, which is complex and difficult, is the only available treatment for suitable patients with PN, who are always in a distressing condition both physically and mentally. Only a few patients may eventually receive surgery. There is therefore a significant unmet medical need for patients with NF1 and inoperable PN in China.

In the clinical setting, treatment with selumetinib in the Phase 1 SPRINT study resulted in confirmed partial responses (PRs; tumour volume decreases from baseline of \geq 20%) in 16/24 (66.7%) children. The response rate was confirmed in SPRINT Phase II Stratum 1. The overall response rate by NCI POB central analysis was 66% (95% CI: 51.2, 78.8; 33/50 patients). Median time to response is 8 cycles. For responders, 42.4% (14/33 patients) achieved response at cycle 5, 72.7% (24/33 patients) achieved response at cycle 9, 97% (32/33 patients) achieved response at cycle 13. Importantly, improvements in PN-related pain and motor impairment demonstrated that selumetinib provided clinical benefit. Selumetinib, therefore, has promising clinical activity for the treatment of NF1 and inoperable PN, as well as a favourable safety profile.

A detailed description of the chemistry, pharmacology, efficacy, and safety of selumetinib is provided in the Investigator's Brochure.

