7. DISCONTINUATION OF TREATMENT AND SUBJECT WITHDRAWAL

7.1 Discontinuation of study treatment

See Table 1 for data to be collected at the time of treatment discontinuation and follow-up, and for any further evaluations that need to be completed. CONFIDENTIAL AND PROPRIETARY 56 of 183 Subjects may discontinue study treatment in the following situations.

- Subject decision. The subject or parent(s)/legal guardian is free to discontinue study treatment at any time without prejudice to further treatment. A subject who discontinues study treatment is normally expected to continue to participate in the study (e.g. for safety follow-up) unless they specifically withdraw their consent to all further participation in any study procedures and assessments (Section 7.3).
- AE that in the opinion of the investigator or AstraZeneca contraindicates further dosing.
- Pregnancy or intent to become pregnant.
- Severe noncompliance with the CSP that, in the opinion of the investigator or AstraZeneca, warrants withdrawal from treatment with IP (e.g. refusal to adhere to scheduled visits).
- Initiation of alternative anticancer therapy including another IMP.
- Subjects who experience a PR and in whom the target PN becomes amenable to surgery.
- Subjects who experience disease progression.

Subjects who achieved a PR of their PN and have subsequently had PN regrowth that meets the criteria for disease progression ($\geq 20\%$ increase from best response) may be permitted to remain on study treatment as long as their PN remains less than 20% above baseline volume and they are receiving clinical benefit in the absence of significant toxicity. These patients will still be considered to have progressive disease for the purpose of analysis of the trial endpoints. PN volume assessments will continue as described in the schedule of assessments and if PN volume increases to $\geq 20\%$ above baseline, study treatment will be discontinued.

• It is deemed in the best interest of the patient, in this instance the sponsor should be notified and the reasons for discontinuation should be noted in the CRF.

Please note that discontinuation from study treatment is NOT the same thing as a complete withdrawal from the study.

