7.1.2 Rechallenge

Dosing may be restarted following interruption as described in Section 6.6.

7.1.3 **Procedures for discontinuation of study treatment**

Subjects or his/her parent(s)/legal guardian are free to discontinue IP or withdraw from the study at any time without prejudice to further treatment. Procedures to follow for study withdrawal are detailed below.

The investigator should instruct the subject or his/her parent(s)/legal guardian to contact the site before or at the time study treatment is stopped. A subject or his/her parent(s)/legal guardian who decides to discontinue study treatment will always be asked about the reason(s) and the presence of any AEs. The date of last intake of study treatment should be documented in the eCRF. All study treatment should be returned by the subject at their next on-site study visit or unscheduled visit. Subjects permanently discontinuing study treatment should be given locally available standard of care therapy, at the discretion of the investigator.

Discontinuation of study treatment, for any reason, does not impact on the subject's participation in the study. The subject should continue attending subsequent study visits and data collection should continue according to the study protocol. Subjects who discontinue study treatment due to reasons other than disease progression will continue to undergo tumour assessments for approximately 1 year, if clinically applicable, and the assessment schedule should continue per the regular tumour assessment interval. If the subject or his/her parent(s)/legal guardian does not agree to continue in-person study visits, a modified follow-up must be arranged to ensure the collection of endpoints and safety information. This could be a telephone contact with the subject or his/her parent(s)/legal guardian, a contact with a relative or treating physician, or information from medical records. The approach taken should be recorded in the medical records. A subject or his/her parent(s)/legal guardian who agrees to modified follow-up is not considered to have withdrawn consent or to have withdrawn from the study.

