- Identify and select the inoperable target PN (plus a maximum of 1 additional nontarget PN) for 3D MRI evaluation. Should there be more than 2 inoperable PNs that meet the criteria for selection, the 2 most clinically relevant PNs will be followed by 3D MRI analysis.
- Perform MRI sequences on the selected index lesions as outlined in the MRI acquisition protocols.

On study imaging evaluation:

Unless clinically indicated otherwise, and as defined in Table 1, 3D volumetric MRI of the target and nontarget PNs should be performed at every 4 cycles (16 ± 1 weeks) relative to the date of first dose for the first 2 years (24 cycles). From the end of Cycle 24, tumour assessments will be performed every 6 cycles (24 ± 1 weeks), as long as the subject remains on study treatment or until disease progression. Subjects who discontinue study treatment due to reasons other than disease progression will continue to undergo tumour assessments for

approximately 1 year, if clinically applicable, and the assessment schedule should continue per the regular tumour assessment interval.

- Complete response (CR): disappearance of the target lesion.
- PR: decrease in the volume of the target PN by 20% or more compared to baseline. The PR is considered unconfirmed at the first detection and confirmed when observed again at a consecutive scan within 3 to 6 months.
- Stable disease: insufficient volume change to qualify for either PR or PD.
- PD: increase in the volume of the target PN by 20% or more compared to baseline or the time of best response after documenting a PR. The appearance of new PN (with the exception of new discrete subcutaneous neurofibromas as noted below) or unequivocal progression of an existing nontarget PN is also considered PD. In this study unequivocal progression is defined as an increase in the volume of the non-target PN by 20% or more compared to baseline.

The clinical appearance of new discrete subcutaneous neurofibromas does not qualify for disease progression. Worsening of existing symptoms or the appearance of new symptoms that persist for more than 7 days and that are felt to be definitely related to the PN should be evaluated by repeating the MRI. Subjects should not be classified as having PD solely on the basis of new or increased symptoms

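### The best overall response window does not stop at surgery on the target PN or at other PN-directed therapy, so a post-surgery scan can create or confirm a response counted in ORR

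*Protocol*

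**What the plan says.** Protocol Section 9.4.3.1.1 defines ORR as the proportion with a CR or a confirmed PR. That definition carries no time window of its own. The only window in the section is the one for BOR: "Best overall response (BOR) is defined as the best response recorded from the start of the treatment until progression or the last evaluable MRI assessment", the latter applying when there is no progression.

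Section 8.1.1 defines PR by a fall of at least 20% in target PN volume from baseline, and adds: "The PR is considered unconfirmed at the first detection and confirmed when observed again at a consecutive scan within 3 to 6 months". CR is the disappearance of the target lesion. ORR asks for confirmation of a PR but not of a CR. Neither definition requires the scan to precede another intervention.

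Section 7.1 lists among the reasons to stop treatment:

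- "Subjects who experience a PR and in whom the target PN becomes amenable to surgery"
- "Initiation of alternative anticancer therapy including another IMP"

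Section 7.1.3 then says: "Subjects permanently discontinuing study treatment should be given locally available standard of care therapy, at the discretion of the investigator". On imaging it says: "Subjects who discontinue study treatment due to reasons other than disease progression will continue to undergo tumour assessments for approximately 1 year, if clinically applicable", at the regular interval. Section 2.2 describes surgery in China: "Debulking surgery, which is complex and difficult, is the only available treatment for suitable patients with PN".

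**The concern.** ORR is meant to describe what selumetinib does to PN volume. Once the target PN has been partly or wholly resected, its volume no longer measures that, yet the stated window still admits the scan. The protocol itself sets up the sequence: a PR, not necessarily confirmed, makes surgery possible; treatment stops; scans continue; and the next scan falls within the confirmation window.

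This is more than a detail left open. The protocol fixes an end to the window, and that end is later than it should be. For ORR and BOR the error can run only towards a better result, because resection removes volume. With 16 subjects per cohort, one such case shows in the headline figure, which readers will set beside the 66% that the protocol quotes from SPRINT Phase II Stratum 1.

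**Working it through.** **Inputs**

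- 16 subjects per cohort (Section 9.2).
- ORR reported with a two-sided 95% Clopper-Pearson interval (Section 9.5.3).
- MRI every 16 ± 1 weeks to Cycle 24, then every 24 ± 1 weeks (Section 8.1.1).
- PR at 80% of baseline volume or less, confirmed at the consecutive scan within 3 to 6 months (Section 8.1.1).
- Comparator: 33/50 confirmed PR (Sections 2.2 and 4.3) and 4/50 unconfirmed PR (Section 4.3).
- Number of subjects whose response would rest on a post-surgery scan: not in the documents. Illustrative range 0 to 2.

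**1. Reproduce the protocol's figure.** Clopper-Pearson for 33/50 gives 66.0% (51.2, 78.8), as stated. The trial's own sample size comes from a guideline minimum, so there is no power calculation to reproduce.

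**2. Does the next scheduled scan fall in the confirmation window?** Months = weeks × 7 / 30.4375.

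- To Cycle 24: 15 weeks = 3.4 months, 17 weeks = 3.9 months.
- After Cycle 24: 23 weeks = 5.3 months, 25 weeks = 5.7 months.

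Both lie inside 3 to 6 months. If surgery falls between a first PR and the next scan, the post-surgery scan is the confirming scan. A year of follow-up at 16-week intervals holds 52/16 = 3.25, so about 3 scans. That is also enough for a new PR to appear and be confirmed after surgery.

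**3. How much resection makes a non-responder a PR by volume?** The fraction to remove is 1 − 80/v, where v is the current volume as a percentage of baseline.

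| v | Fraction to remove |
|---|---|
| 85 | 5.9% |
| 90 | 11.1% |
| 100 | 20.0% |
| 110 | 27.3% |

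**4. Effect on cohort ORR.** Each affected subject moves ORR by 1/16 = 6.25 percentage points.

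| Responders | ORR | Exact 95% CI |
|---|---|---|
| 9/16 | 56.3% | 29.9 to 80.2 |
| 10/16 | 62.5% | 35.4 to 84.8 |
| 11/16 | 68.8% | 41.3 to 89.0 |

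If 11 responses are counted as written and one rests on a post-surgery scan, the proposed window gives 10/16; if two do, 9/16. The step from 10 to 11 crosses the 66% comparator.

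**5. How large is the pool in which the confirming-scan route could arise?** At the comparator's unconfirmed-PR rate of 4/50 = 8%, 16 × 0.08 = 1.28 subjects are expected per cohort, and the chance of at least one is 1 − 0.92^16 = 74%. These are subjects with an unconfirmed PR, not subjects operated on, so the number affected is smaller and may be zero.

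**The case against.** **The SAP may deal with it.** Section 9.5 calls itself a summary and leaves the handling of missing, unused and spurious data to the SAP, which is not at hand. That answers complaints about missing censoring rules. It does not answer this one: an SAP that shortened the BOR window would be changing an end point that the protocol states.

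**The qualifiers may already exclude such scans.** Post-treatment MRI is done only if clinically applicable, and the last MRI must be evaluable. Both terms leave room to drop post-surgery scans, but neither is defined to do so. The first governs whether a scan is taken, not whether it counts. Section 8.1.1 makes a subject evaluable for response after a single dose, and inclusion criterion 6 accepts an incompletely resected PN as measurable.

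**Surgery will be uncommon, and often harmless to ORR.** This stands. Entry requires an inoperable PN, exclusion criterion 14 bars planned major surgery during treatment, and Section 2.2 expects few patients to reach surgery. The surgical case in Section 7.1 concerns subjects who already have a PR; if it was confirmed beforehand, ORR does not change.

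Three stronger readings are tempting and are not supported:

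- *That debulking is the standard of care given to everyone who stops.* Section 7.1.3 does not define standard of care, and Section 2.2 confines surgery to suitable patients.
- *That another drug would commonly produce false responses.* The wording allows it, but Section 2.2 says no systemic therapy has been shown to shrink these tumours reliably and lastingly.
- *That DoR, PFS and TTP are lengthened as well.* Sections 9.4.3.1.2 to 9.4.3.1.4 give conventional event definitions, and censoring is ordinary SAP content. The direction is also uncertain. After a PR, progression is measured from best response: at 78% of baseline the threshold is 1.2 × 78 = 93.6%, but after removing half the lesion it is 1.2 × 39 = 46.8%, so regrowth could trigger progression sooner. A lesion that is almost gone may never show progression.

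**Conclusion.** The point holds for BOR and ORR. As stated, the window lets a scan after surgery on the target PN supply the confirmation of a PR, or count as a new PR or CR. The size is 6.25 percentage points of cohort ORR per affected subject. The figures for one or two subjects are illustrations; no document gives a count.

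This rests on reading the BOR window as the window for ORR, since Section 9.4.3.1.1 offers no other, and on taking evaluable in its undefined sense. ORR is secondary and descriptive and no hypothesis is tested (Section 9.1), so neither error rate nor power is affected. What is at stake is whether the reported response rate can be attributed to selumetinib. No conclusion is drawn about DoR, PFS or TTP.

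**What to change.** In Section 9.4.3.1.1, state that BOR and ORR use MRI assessments up to the earliest of:

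- progression;
- surgery on the target PN;
- start of other PN-directed therapy;
- the last evaluable MRI.

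State that a PR must be confirmed by a scan within that window. List later scans, and report a sensitivity analysis of ORR using all scans. Leave the handling of DoR, PFS and TTP at these events to the SAP, where the choice between censoring and using all follow-up can be argued.

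The cost is a short text change, one derived date per subject and one extra table. Treatment and the scan schedule do not change. The downside is that a few responses may leave the headline ORR, including a true PR whose confirming scan would have followed surgery; the sensitivity analysis keeps those visible.

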9.4.3.1.2 Duration of response

Duration of response (DoR) is defined as the time from the date of the first documented response (which is subsequently confirmed) until the date of documented progression or death in the absence of disease progression, as determined by independent central review and investigator per REiNS criteria.

9.4.3.1.3 **Progression free survival**

Progression-free disease (PFS) is defined as the time from the date of first dose until progression per REiNS criteria as assessed by independent central review and investigator, or death due to any cause.

9.4.3.1.4 Time to progression

Time to progression (TTP) is defined as the time from the date of first dose until progression per REiNS criteria as assessed by independent central review and investigator.

